12.2.3 Multiplicity adjustments for the primary and key secondary variables

The proposed basic testing strategy will be in the order as follows: 1) primary endpoint of MADRS change from baseline at Week 6; 2) key secondary endpoint of MADRS change from baseline at Week 12; 3) key secondary endpoint of sustained response from Week 6 to Week 12. The overall, family-wise type-I error rate at $\alpha=0.05$ ($\alpha=0.025$ one-sided) will be equally split in half ($\alpha=0.0125$ one-sided) for each of the 2 doses (50 mg and 100 mg) versus placebo. For each dose versus placebo, if the primary endpoint of MADRS change from baseline at Week 6 is significant, then its test mass is recycled to test the first key secondary endpoint of MADRS change from baseline at Week 12. If the first key secondary endpoint is significant, then its test mass is recycled to test the second key secondary endpoint of sustained response from Week 6 to Week 12. The testing strategy is displayed graphically in [Figure 2](#). This approach controls the overall family-wise type-I error rate at $\alpha=0.05$ ($\alpha=0.025$ one-sided) in the strong sense.

Figure 2 Multiplicity adjustment strategy

12.2.4 Safety analyses

Adverse events will be coded using the MedDRA. For each study treatment, numbers of events and crude incidence rates will be tabulated by preferred term and system organ class. An event that occurred 1 or more times on the date of, or subsequent to, randomization will contribute 1 observation to the numerator of the crude incidence rate. The denominator of the rate will comprise all randomized patients exposed to the study treatment. If the intensity or seriousness of the AE changes, the overall intensity or seriousness will be the maximum intensity or seriousness of the multiple occurrences.

Serious adverse events, AEs leading to death, and AEs leading to withdrawal of patients will be tabulated for each treatment group. Commonly occurring AEs, ie, those which occur in 5% or more of the patients in either treatment group, will be summarized using descriptive statistics.

Descriptive statistics will be used to present the safety outcomes including incidences and severity of AEs and SAEs; incidences of AEs leading to treatment discontinuation and study withdrawal, incidences of AEs associated with suicidality, and incidences of OAEs; changes from baseline in physical examination results, weight, BMI, vital signs, clinical laboratory test

results, and ECG results; suicidality as assessed by C-SSRS; and changes from baseline in CADSS total scores.

All laboratory test results, vital signs, ECG results, weight, and BMI will be summarized for each treatment group using descriptive statistics at each visit for raw numbers and change from baseline. The proportions of patients who have a weight gain $\geq 7\%$ compared with baseline will be tabulated.

Suicidality measures based on the STS and the C-SSRS will be summarized for each treatment group using descriptive statistics at each assessment.

The results of the PK and pharmacogenetic analyses will be presented in reports separate from the CSR.

12.2.5 Interim analyses

No interim analysis for efficacy is planned.

12.2.6 Handling of missing data

Despite efforts to minimize missing data in the design and conduct of this study, the problem of missing data is unavoidable in any MDD study due to patient dropout. Based on the previous Phase II study of D6702C00009 data, estimates for dropouts in the current study are approximately 14% by Week 6 and an additional 10% dropout by Week 12. These missing data will have some impact on the efficacy. The degree of the impact on the efficacy analysis will depend on the analysis method used, dropout reasons, amount and pattern of missing data, and the magnitude of expected treatment effect.

To mitigate the effect of dropouts on the efficacy analysis, the proposed analysis plan includes multiple layers to capture as complete a dataset as possible. First, patients will be asked to return to the clinic to collect primary and key secondary endpoint measures for the intended study period of 12 weeks even after the patient discontinues the study in order to provide the most complete dataset possible of all randomized patients. This retrieved dropout information will be included in the main efficacy analysis. Second, the reasons, proportions, and timing of patient withdrawal from the study for each treatment group will be carefully collected and adequately described and presented to help evaluate the scale of the missing data. Third, a MMRM analysis is proposed for the primary analysis. The MMRM is considered as a method of handling missing data, which does not employ explicit imputation. The MMRM methods provide a valid approach in the case that data are missing at random (MAR). The MAR is a less restricted assumption than the most restricted missing completely at random (MCAR) assumption upon which last observation carried forward (LOCF) and complete case analysis are based.

Nevertheless, missing not at random (MNAR) can never be ruled out. As indicated in regulatory guidelines and published literature that all methods require untestable assumptions because the “missingness” mechanism involves assumptions about the relationships among variables with missing values and results often vary depending on the assumptions made about

these relationships. Furthermore, the validity of these assumptions cannot generally be determined from the collected data. Therefore, there is no single correct method for handling missing data and specific sensitivity analyses under MNAR will be proposed to assess the robustness of the primary MMRM results. These MNAR sensitivity analyses, along with their justifications, including some type of Pattern-Mixture approach, will be detailed in the SAP.

In general, unless otherwise indicated, no data imputation will be done for the missing values.

[figure not shown]
12.3 Determination of sample size

The sample size calculation in this study was done to ensure a 90% power to show that at least 1 of the 2 AZD6765 doses will be better than placebo with regard to the primary outcome variable, change in MADRS total score from baseline to Week 6. The sample size was calculated by assuming an anticipated difference of 5.5 units from placebo and a standard deviation of 10 for the change in MADRS total score from baseline to Week 6. Based on the Bonferroni multiplicity adjustment, the one-sided significance level is planned at 1.25%, which yielded a planned sample size of 84 patients per arm required at Week 6 for the primary analysis. Assuming approximately 10% of information will be lost at Week 6 due to dropout, it is estimated that 282 patients (94 patients per arm) will need to be randomized.

The assumptions for the sample size estimation were based on the results of the targeted subgroup (HAM-D-17 ≥ 24 , CGI-S ≥ 5 , QIDS-SR-16 ≥ 19) from previous a Phase II study of D6702C00009. The average treatment difference observed for AZD6765 100 mg and 150 mg versus placebo at Week 3 in this targeted subgroup was about 5.5. With the continuous once-a-week iv treatment, we expect the same treatment effect can be maintained to the primary time point at Week 6. The observed SD in this targeted subgroup was about 10 across the 3 treatment groups from this study. The dropout rates for D6702C00009 study was about 6% at Week 3 and about 19% at Week 8, so we expect about 14% dropout rate by Week 6 and an additional 10% dropout by Week 12. The MMRM approach on the primary variable uses the correlation between visits that allows us to recover some lost information. The correlations among these visits were between 0.4 and 0.7 in Study D6702C00009, so it seems to be reasonable to assume this correlation to be about 0.5. With this assumption, we expect to recover about 30% of the lost information by the MMRM approach (Lu et al 2008).

The sample size for this study was selected to be consistent with the research hypothesis.

The number of patients that will agree to participate in the genetic research is unknown. It is therefore not possible to establish whether sufficient data will be collected to allow a formal statistical evaluation or whether only descriptive statistics will be generated. A SAP will be prepared where appropriate.

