The sample size calculation in this study was based on the observed 5.5 difference of primary endpoint for AZD6765 100 mg versus placebo at Week 3 from previous Phase II study (D6702C00009). However, we later realized that this assumption may be too optimistic as the collection of the primary efficacy data in this study is one week after the most recent infusion which is different than the collection of primary efficacy data at 2 hours after the start of most recent infusion in study D6702C00009. A more conservative estimate of the treatment effect would be from Week 4 and 5 (1 & 2 weeks after the last infusion) data of the previous study D6702C00009. The estimates of the treatment effect from Week 4 and 5 for AZD6765 100 mg versus placebo were 4.4 and 4.9 (LSM difference), respectively. Therefore, an estimate of 4.5 is a more likely estimate of the treatment effect we will see in the current study at Week 6. To compensate for the loss of power due to the more conservative effect size, we propose to modify our multiplicity adjustment procedure for the primary and key secondary variables as indicated in the previous section. The order of proposed testing sequence is based on the confidence we have on the dose and likelihood of success on these hypotheses. Without any modification to the multiplicity adjustment procedure, the power will reduce from 90% to about 74% for the first hypothesis test of AZD6765 100 mg versus placebo at Week 6 assuming the current sample size, and the more conservative effect size. With the proposed modified multiplicity adjustment procedure, the power will improve to about 82% for the same first hypothesis test.

Persons who initiated the Administrative Change:

[REDACTED]

Signed agreement to the Administrative Change:

I hereby approve the Administrative Change to the Clinical Study Protocol.

Study Code: D6702C00031

.....
Date

(Day Month, Year)

.....
AstraZeneca Study Leader

[REDACTED]
[REDACTED]
[REDACTED]

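### Section 12.3 still states 90% power for at least one dose at 5.5 points and one-sided 1.25%; under Administrative Change 1 the power is about 82–83%, and it belongs to the 100 mg Week 6 test

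*Protocol*

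**What the plan says.** Protocol Section 12.3 states that the calculation was "done to ensure a 90% power to show that at least 1 of the 2 AZD6765 doses will be better than placebo". Its inputs are an SD of 10 for the Week 6 change and, for the effect, "assuming an anticipated difference of 5.5 units from placebo". On the level it says: "Based on the Bonferroni multiplicity adjustment, the one-sided significance level is planned at 1.25" per cent. The result is a "planned sample size of 84 patients per arm required at Week 6", raised to 94 per arm (282 in total) for about 10% lost information.

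Administrative Change 1, appended to the protocol, lists Section 12.2.3 as the section affected. Its revised text is a six-step fixed sequence, each step at two-sided 0.05:

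1. 100 mg, Week 6
2. 100 mg, Week 12
3. 50 mg, Week 6
4. 50 mg, Week 12
5. 100 mg, sustained response
6. 50 mg, sustained response

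After the first non-significant step, all later tests count as non-significant. The stated reason is that 5.5 may be too optimistic: "Therefore, an estimate of 4.5 is a more likely estimate of the treatment effect we will see in the current study at Week 6". For the 100 mg Week 6 test it reports about 74% power if the procedure is left alone, and then: "With the proposed modified multiplicity adjustment procedure, the power will improve to about 82% for the same first hypothesis test". It does not revise Section 12.3.

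**The concern.** Two power statements stand in one protocol, and they differ in effect size (5.5 or 4.5), in level (one-sided 1.25% or 2.5%), in the hypothesis powered (either dose, or 100 mg alone) and in the result (90% or about 82%). Section 12.3 is where a reader looks for the power. Someone who reads only that section would judge a negative trial against 90% for either dose.

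Under the fixed sequence, 50 mg can no longer succeed alone. Its primary comparison stands third, behind two 100 mg tests. Nothing in Section 12.3 warns that the stated power does not extend to it.

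**Working it through.** **Inputs.** Section 12.3: SD 10, 84 effective patients per arm, 5.5 points, one-sided 0.0125. Administrative Change 1: 4.5 points, two-sided 0.05 (one-sided 0.025). Allocation is 1:1:1.

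Standard error of a difference = 10 × √(2/84) = 1.543. Normal-approximation power = Φ(difference/1.543 − z), with z = 2.241 at one-sided 0.0125 and 1.960 at one-sided 0.025. The t figures use the noncentral t with 166 degrees of freedom.

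**Step 1: reproduce the plan's own figures.**
- Patients per arm = 2 × 10² × (2.241 + 1.282)² / 5.5² = 82.1, so 83 by the normal formula. The stated 84 is consistent with this.
- 84/0.9 = 93.3, so 94 per arm and 282 in total, as stated.
- Power at 5.5 and one-sided 0.0125: 5.5/1.543 = 3.564; Φ(3.564 − 2.241) = 90.7% (t: 90.3%). The stated 90% is reproduced, and it is the power of **one** dose comparison.

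**Step 2: the figures in Administrative Change 1.**
- 4.5 at one-sided 0.0125: 4.5/1.543 = 2.916; Φ(2.916 − 2.241) = 75.0% (t: 74.3%). Stated: about 74%.
- 4.5 at one-sided 0.025: Φ(2.916 − 1.960) = 83.1% (t: 82.6%). Stated: about 82%.
- At the earlier study's Week 4 and Week 5 estimates, with one-sided 0.025: 4.4 gives 81.4% (t: 80.9%) and 4.9 gives 88.8% (t: 88.4%).

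**Step 3: power for at least one dose.** Under the fixed sequence it equals the Step 2 figure, 82–83%, because a failed 100 mg Week 6 test stops everything after it. Under the old split, the two test statistics share the placebo arm and have correlation 0.5, so the power is 1 − P(both below 2.241). With 5.5 in both doses that is 97.1%. With 5.5 in one dose and 0 in the other it is 90.7%.

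With 100 mg at 4.5 and the 50 mg effect varied (an assumption, since the protocol gives no 50 mg effect):

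| 50 mg effect | Old split, at least one dose | Fixed sequence |
|---|---|---|
| 0 | 75.0% | 83.1% |
| 2 | 76.0% | 83.1% |
| 3 | 78.8% | 83.1% |
| 3.5 | 81.3% | 83.1% |
| 4 | 84.4% | 83.1% |
| 4.5 | 88.0% | 83.1% |

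The two procedures are equal at a 50 mg effect of about 3.8 points.

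**Step 4: the 50 mg Week 6 test, as illustration only.** Assume 4.5 at every test. Passing both Week 6 tests has probability 73.0% before the 100 mg Week 12 gate is counted, so that is an upper limit. For the gate, use the 14% + 10% = 24% dropout by Week 12 with 30% of the lost information recovered (both from Section 12.3; applying the recovery to Week 12 is an assumption). That leaves 94 × (1 − 0.24 × 0.7) = 78.2 effective patients per arm. With a between-week correlation of 0.4, 0.5 or 0.7 (the range in Section 12.3), the probability of passing the first three steps is about 62%, 63% or 65%.

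**The case against.** The strongest reply is that nothing has been miscalculated or hidden. Every stated figure reproduces. Section 12.3 is written in the past tense and remains a true record of how 282 was reached. The sponsor states the lower effect and the 82% in its reason for the change. All of this stands, and it limits the seriousness. It does not remove the inconsistency: the change document replaces the procedure on which Section 12.3 rests, yet leaves that section's level, effect and power standing without a cross-reference. Nor is this a comparison of superseded text with current text. The revised wording is meant to replace the body wording, and Section 12.3 is not among the text replaced.

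Three stronger readings are tempting and should not be drawn.

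- A reader might infer that the sponsor's rationale compares unlike quantities, because Section 12.3 attaches the 90% to either dose and the change document attaches 74% and 82% to 100 mg. Step 1 shows that the 90% is itself a single-comparison figure, so the three are like for like. Only the label in Section 12.3 is loose.
- A reader might infer that the change lowers the chance of showing at least one dose unless 50 mg has little effect. It lowers it only if the 50 mg effect exceeds about 3.8 points. Below that, the change raises it.
- A reader might infer that a 50 mg power should be a design figure in Section 12.3. The depression studies described used 100 mg and 150 mg, so any 50 mg power rests on an assumed effect.

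**Conclusion.** The point holds as a section left out of date. Section 12.3 states 90% for at least one of two doses at 5.5 points and one-sided 1.25%. On the sponsor's revised effect and procedure the figure is about 82–83%. It applies to 100 mg at Week 6 and, through the gating, equally to at least one dose. The overstatement is about 7 to 8 points.

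This rests on SD 10, 84 effective patients per arm, a true 100 mg difference of 4.5, and Administrative Change 1 being in force. Dates are blacked out, but its previous text matches the wording still in the body of Section 12.2.3.

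Severity is minor to moderate. The randomized number and the testing rule in the change document are unaffected, and the current power can be found there by a reader who looks.

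**What to change.** Revise Section 12.3, or add it to the sections affected by Administrative Change 1, as follows.

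- Keep the 5.5-point, one-sided 1.25%, 90% derivation only as the original basis for 84 effective and 94 randomized patients per arm. Describe the 90% as the power of a single dose comparison.
- State the current design: difference 4.5, SD 10, 84 effective patients per arm, fixed sequence at two-sided 0.05, about 82% power for 100 mg versus placebo at Week 6. Add that this is also the power to show at least one dose.
- Say that the 50 mg Week 6 test is third in the sequence and is not covered by that figure. If an illustration is wanted, give about 62–65% and label it as assuming 4.5 at every test.

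The cost is wording only. The stated power becomes less favourable; no extra patients and no change to the analysis are needed.

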13.2 Overdose

In the event of an overdose, the extent of the overdose, causative factors, and medical complications should be determined. No specific treatment is available to reverse the effects of AZD6765. For the AZD6765iv program, any overdoses of AZD6765iv, placebo, or antidepressant therapy in the interval from Visit 2 to the end of follow-up should be recorded. Overdose is defined as a dose ingested (or taken via any other route), confirmed by the patient (if possible), in excess of the total daily dose specified for the patient in their treatment group of the protocol (including prospective antidepressant therapy).

Based on human studies to date, dizziness, lightheadedness, nausea, vomiting, headache, and blurred vision can occur when AZD6765 is administered in excess. In the event of these or other AEs, the patient should be monitored carefully and treated symptomatically. In the event of excessive anxiety or dissociative reactions, a benzodiazepine such as lorazepam can be administered.

An overdose is a dose in excess of the doses specified for the dose group. For recording purposes:

- Use of IP in doses in excess of that specified in the protocol should not be recorded in the eDC system as an AE of “Overdose” unless there are associated symptoms or signs. The associated symptoms or signs will be the AE terms documented in the source documentation and eDC system.
- An overdose with associated SAE(s) must be recorded as the SAE diagnosis/symptoms on the relevant AE forms in the source documentation and eDC system only.
- An overdose with associated non-serious AEs must be recorded as the AE diagnosis/symptoms on the relevant AE forms in the source documentation and in eDC, and on the separate AstraZeneca “Clinical Study Overdose Report Form.” Only overdoses of IP will be reported.
- An overdose without associated symptoms must be only reported on the separate AstraZeneca “Clinical Study Overdose Report Form.”

Information on overdoses in study patients is collected by AstraZeneca or representative and forwarded to AstraZeneca’s clinical patient safety data entry sites. Should a patient experience an overdose during the course of the study (whether accidental or deliberate), the investigator or qualified designee must contact AstraZeneca or representative **within 1 business day**, ie, immediately, but no later than **the end of the next business day** of when the investigator or qualified designee first becoming aware of the overdose.

The designated AstraZeneca representative works with the investigator to ensure that all relevant information is provided to the AstraZeneca patient safety data entry site.

For overdoses associated with SAE, standard reporting timelines apply, see Section 6.4.4. For other overdoses, reporting should be done within 30 days.

13.3 Pregnancy

All outcomes of pregnancy must be reported to AstraZeneca or representative.

13.3.1 Maternal exposure

Requirements for contraception in WOCBP are specified in inclusion criterion #2 (Section 4.1).

If a patient becomes pregnant during the course of the study, the IP should be discontinued immediately.

Pregnancy itself is not regarded as an AE unless there is a suspicion that the IP under study may have interfered with the effectiveness of a contraceptive medication. Congenital abnormalities/birth defects and spontaneous miscarriages should be reported and handled as SAEs. Elective abortions without complications should not be handled as AEs. The outcome of all pregnancies (spontaneous miscarriage, elective termination, normal birth, or congenital abnormality) must be followed up and documented even if the patient was discontinued from the study.

If any pregnancy occurs in the course of the study, then investigators or other site personnel inform appropriate AstraZeneca representatives **within 1 day** ie, immediately, but no later than the **end of the next business day** of when he or she becomes aware of it.

The designated AstraZeneca representative works with the investigator to ensure that all relevant information is provided to the AstraZeneca Patient Safety data entry site within 1 or 5 days for SAEs, see Section 6.4.4, and within 30 days for all other pregnancies.

The same timelines apply when outcome information is available.

13.3.2 Paternal exposure

The outcomes of any conception occurring from the date of the first dose until 1 week after the last dose must be followed up and documented.

Male patients must refrain from fathering a child during the study and **3 months** following the last dose, since the potential for chromosomal aberrations in male gametes, and possible teratogenic effects thereof, have not been thoroughly investigated.

Pregnancy of the patient's partners is not considered to be an AE. However, the outcome of all pregnancies (spontaneous miscarriage, elective termination, normal birth, or congenital abnormality) must be followed up and documented.

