4.1 Inclusion criteria

For inclusion in the study, patients must fulfill the following criteria:

1. Provision of informed consent before initiation of any study-related procedures
2. Patients must provide acceptable proof of identity documentation to confirm initials and date of birth
3. Male and female patients aged 18 to 70 years, inclusive. All male patients who are sexually active must agree to use a double barrier method of contraception (condom with spermicide) from the first dose of IP until 12 weeks after their last dose. All females must have a negative serum pregnancy test. Women of childbearing potential (WOCBP, see below) must use (confirmed by the investigator) a highly effective form of birth control plus the use of a condom by the male sexual partner. The highly effective form of birth control includes: true sexual abstinence, a vasectomized sexual partner, Implanon, female sterilization by tubal occlusion, any

effective IUD/IUS, Depo-Provera™ injections, oral contraceptive, and Evra Patch™ or Nuvaring™. Women should be on a stable method of birth control for a minimum of 3 months as judged by the investigator, prior to randomization and 3 months after the last dose of IP.

Women of non-childbearing potential. Women of non-childbearing potential are defined as women who are either permanently sterilized (hysterectomy, bilateral oophorectomy, or bilateral salpingectomy), or who are postmenopausal. Women will be considered postmenopausal if they are amenorrheic for 12 months prior to randomization without an alternative medical cause. The following age-specific requirements apply:

- Women <50 years old would be considered postmenopausal if they have been amenorrheic for 12 months or more following cessation of exogenous hormonal treatment and follicle stimulating hormone (FSH) levels in the postmenopausal range.
 - Women ≥50 years old would be considered postmenopausal if they have been amenorrheic for 12 months or more following cessation of all exogenous hormonal treatment.
4. Documented clinical diagnosis meeting criteria from the DSM-IV-TR confirmed via the MINI of Major Depressive Disorder: 296.2x MDD, Single Episode or 296.3x MDD, Recurrent.

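### The 1-week window for following up partner conceptions in Section 13.3.2 contradicts the protocol's own 12-week and 3-month post-dose precaution periods and its undated duty to follow all pregnancies

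*Protocol*

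**What the plan says.** **Men.** Section 13.3.2 makes three statements in successive paragraphs.
- A dated follow-up rule: "The outcomes of any conception occurring from the date of the first dose until 1 week after the last dose must be followed up".
- A precaution: male patients must refrain from "fathering a child during the study and 3 months following the last dose". The reason given is "since the potential for chromosomal aberrations in male gametes, and possible teratogenic effects thereof, have not been thoroughly investigated".
- A closing sentence that requires the outcome of every partner pregnancy to be followed and documented, with no time limit.

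Inclusion criterion 3 in Section 4.1 requires contraception in sexually active men "from the first dose of IP until 12 weeks after their last dose".

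**Women.** Inclusion criterion 3 asks for a stable method of birth control for a minimum of 3 months "prior to randomization and 3 months after the last dose of IP". Section 13.3.1 sets the notification duty, due by the end of the next business day: "If any pregnancy occurs in the course of the study, then investigators or other site personnel inform appropriate AstraZeneca representatives". The same section says that the outcome of all pregnancies "must be followed up and documented even if the patient was discontinued from the study".

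**Both.** Section 13.3 opens with a general rule that has no window: "All outcomes of pregnancy must be reported to AstraZeneca or representative".

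**Related text.** The last scheduled visit is 14 (± 4) days after the last dose (Section 3.1.3). Section 9.5 defines the end of the study once, for the whole trial, as the last patient's last visit. Section 13.3.1 sends the reader to inclusion criterion #2 for contraception. Criterion 2 is proof of identity; contraception is in criterion 3.

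**The concern.** A protocol that asks patients to avoid conception for a stated time after dosing should make clear whether a conception in that time is reported. Section 13.3.2 gives a 3-month precaution based on uninvestigated gamete risk, next to a follow-up rule that stops at 1 week. Section 1.4 adds that embryofetal toxicity was seen in rats and rabbits and that its clinical relevance is unknown.

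What is at stake is how completely exposed pregnancies are captured. Contraception is mandatory, so few are likely. If sites apply different rules to those few, an absence of reports from the later post-dose weeks could not be read as reassurance. The efficacy analyses are not affected.

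**Working it through.** The protocol gives no figure of its own to reproduce. The check compares the windows and measures how far they differ.

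**Inputs**
- Dated paternal follow-up: 1 week after the last dose (13.3.2).
- Male precaution: 12 weeks (4.1, criterion 3) or 3 months (13.3.2).
- Female precaution: 3 months (4.1, criterion 3).
- Last visit: day 10 to 18 after the last dose (3.1.3).
- Assumptions: 3 months = 13 weeks = 91 days; a completer's last infusion falls 11 to 12 weeks after the first, since it is given in Week 12.

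**Men, post-dose period.** Share covered by the dated rule = follow-up weeks / precaution weeks.
- Against 12 weeks: 1/12 = 8.3% covered, 11/12 = 91.7% outside.
- Against 3 months: 1/13 = 7.7% covered, 12/13 = 92.3% outside.

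**Men, from first dose to end of precaution.** Share covered = (dosing weeks + 1) / (dosing weeks + 12 or 13).

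| Patient | Covered | Outside |
|---|---|---|
| Completer, last dose at week 11 | 12/23 = 52.2%; 12/24 = 50.0% | 47.8%; 50.0% |
| Completer, last dose at week 12 | 13/24 = 54.2%; 13/25 = 52.0% | 45.8%; 48.0% |
| Stops after 3 weeks | 4/15 = 26.7%; 4/16 = 25.0% | 73.3%; 75.0% |
| Single dose | 1/12 = 8.3%; 1/13 = 7.7% | 91.7%; 92.3% |

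**Do the paternal statements fit together?** If the closing sentence of 13.3.2 has no time limit, the 1-week sentence does nothing. If the 1-week sentence does something, it limits the closing sentence. Take a partner conception 5 weeks after the last dose. It falls inside both precaution periods and outside the dated rule, and the closing sentence would include it. The text does not say which statement governs.

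**Women.** The notification duty depends on what the study period means for one patient, which the protocol does not define.
- If it ends at her last visit, 10/91 = 11.0% to 18/91 = 19.8% of the 3 months is covered. That leaves 91 − 18 = 73 to 91 − 10 = 81 days, or 80% to 89%, without an explicit trigger.
- If it ends with the whole trial (Section 9.5), coverage depends on when she enrolled and may be complete for an early patient.

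Neither reading is tied to the 3-month period.

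**The case against.** The strongest reply is that the protocol already asks for everything. Sections 13.3, 13.3.1 and 13.3.2 each contain a duty to report or follow pregnancies that has no time limit, and 13.3.1 extends it to patients who have discontinued. This stands to an important extent. A reader might infer that conceptions are followed only to 1 week and maternal pregnancies only during the study. The documents do not support that: the undated duties point the other way, and the 13.3.1 phrase about the study period triggers prompt notification without limiting outcome follow-up. The reply does not remove the paternal contradiction, because a dated rule and an undated rule on the same subject still stand in one section.

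A reader might also infer that most at-risk exposures go unreported. That does not follow. The 92% is a share of post-dose calendar weeks. Over the whole period from first dose, 46% to 50% lies outside the dated window for a completer, and the documents give no conception rates from which to count exposures.

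For women the objection is stronger. The 80% to 89% holds on only one of two readings. The gamete rationale concerns men. With a terminal half-life of 11 to 14 hours (Section 1.1.2.2), 10 days is at least 240/14 ≈ 17 half-lives, so a conception after the last visit would involve very little remaining drug. The maternal point is therefore only that the trigger is unclear.

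**Conclusion.** The point holds as an internal contradiction in safety reporting. The dated conception window in 13.3.2 conflicts with the 3-month precaution and the undated all-pregnancies duty in the same section, and with the 12-week period in criterion 3. It covers 1 of 12 to 13 post-dose weeks, about 8%, with 3 months taken as 13 weeks. The conflict leaves the handling of partner conceptions in weeks 2 to 12 to each site's reading.

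Secondarily, 13.3.1 does not say whether prompt notification applies to a pregnancy that arises after the patient's last visit but within the 3-month contraception period. No single percentage can be put on this, because it depends on how the study period is read. The cross-reference to criterion #2 is a plain error.

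Confidence is high for the paternal conflict and the cross-reference, and lower for the maternal trigger. The matter deserves correction but does not threaten the trial's primary conclusions.

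**What to change.** Reconcile inclusion criterion 3 with Sections 13.3.1 and 13.3.2.
- Make the dated conception rule in 13.3.2 consistent with whatever post-dose precaution period the sponsor keeps, and with the undated duties in 13.3 and 13.3.2.
- Settle whether the male period is 12 weeks or 3 months, since the two sections differ.
- State in 13.3.1 whether the notification duty includes a pregnancy after the patient's last visit but within the contraception period.
- Correct the 13.3.1 cross-reference from criterion #2 to criterion 3.

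Which period is right is for the sponsor to decide. The cost is amendment wording, with matching consent wording where needed, and possibly a few more reports to follow. No visits or tests are added.
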